5.5.2. Alcohol Restrictions

Patients will limit alcohol consumption throughout the course of the study. Alcohol is limited to no more than 2 units per day (unit: 1 glass of wine [approximately 125 mL] = 1 measure of spirits [approximately 1 fluid ounce] = $\frac{1}{2}$ pint of beer [approximately 284 mL]) for the duration of the study.

5.5.3. Dietary Restrictions

Patients should refrain from consumption of foods with high oxalate content, including, but not limited to, chocolate, rhubarb, spinach, and beet root, for 1 week prior to assessments of urinary and plasma oxalate.

6. STUDY ASSESSMENTS

The schedules of study assessments is provided in [Table 1](#), [Table 2](#), [Table 3](#), and [Table 4](#).

Where applicable country and local regulations and infrastructure allow for home healthcare, healthcare may take place at a location other than the clinical trial site to perform study assessments, which may include pregnancy testing (urine or serum), clinical laboratory assessments, urine collections, DNA testing, symptom-directed physical examination / body system assessment, vital signs, body weight, height, PK and PD blood collection, blood collection for vitamin B6 levels, ADA and exploratory analyses (blood and urine) assessments, at all timepoints as specified in the Schedule of Assessments.

6.1. Screening Assessments

An informed consent form (ICF) or assent form in the case of patients under the age of legal consent that has been approved by the appropriate Institutional Review Board (IRB)/Independent Ethics Committee (IEC) must be signed by the patient (or legal guardian if under the age of legal consent) before the Screening procedures are initiated. All patients (or their legal guardians if under the age of legal consent) will be given a copy of the signed and dated ICF and/or assent form. In the case when a patient reaches the legal age of consent during the study, the investigator must obtain the patient's informed consent prior to performing any further study interventions and/or procedures involving that patient (see [Section 8.1.1](#)).

Patients will be screened to ensure that they meet all the inclusion criteria and none of the exclusion criteria (see [Section 4.1](#) and [Section 4.2](#)).

Patient demographic data and medical history/disease history will be obtained. Any changes to medical history occurring between the screening assessment and Day 1 will be updated prior to study drug administration.

A blood sample for PH1/AGXT mutation analysis will be collected for patients who do not have documented PH1 genetic analysis to confirm eligibility.

During the screening period, at least 3 separate 24-hour urine collections will be completed to assess urinary oxalate excretion. Patients are strongly encouraged to complete these collections during supervised visits unless they are already familiar with the collection procedures. At least 2 of these collections need to be confirmed to be valid collections (see Section 6.3.1.1) prior to receiving study drug on Day 1. The mean urinary oxalate excretion from the first 2 valid baseline collections will be used to determine eligibility for the study (see Section 4.1) and randomization stratification.

6.1.1. Retesting

If in the Investigator's judgement, the screening laboratory abnormalities are likely to be transient, then laboratory tests, excluding urinary oxalate, may be repeated. The investigator's rationale is to be documented. Laboratory values can be retested once during Screening as long as the patient can be evaluated for eligibility and randomized within the allowed Screening period.

6.1.2. Rescreening

A patient who does not meet all study eligibility criteria may be allowed to return for rescreening if appropriate in the opinion of the investigator and after consultation with the Medical Monitor. A patient will be re-consented and assent obtained (if applicable) if rescreening occurs outside of the 60-day screening window. In this case, all screening procedures must be repeated.

6.2. Efficacy Assessments

The efficacy of lumasiran will be assessed by evaluating the percent change in 24-hour urinary oxalate excretion determined from 24-hour urine sample collections described in Section 6.3.1.

6.3. Pharmacodynamic and Renal Assessments

Urine and blood samples will be collected for assessment of PD parameters (plasma and urinary oxalate and glycolate concentrations) and renal parameters at the time points specified in the Schedules of Assessments (Table 1 and Table 2). All blood and urine samples will be collected prior to dosing, if applicable.

Where local regulations allow and infrastructure is in place, home nursing may be used to collect urine samples or for repeat blood sample collection, if necessary.

6.3.1. 24-hour Urine Collections to determine Urinary Oxalate Excretion

Urinary oxalate excretion will be determined from 24-hour urine sample collections to be completed at the time points specified in the Schedules of Assessment (Table 1 and Table 2) to assess urinary oxalate excretion. Urinary oxalate concentrations will be analyzed centrally using a validated assay. The duration of collection and volume of urine in the collection will be recorded in the eCRF. An aliquot of the 24-hour urine collection will also be used to determine urinary creatinine content to determine if the 24-hour urine collections need to be repeated (see Section 6.3.1.1).

Single void collections for random urine sample for PD analysis should be collected as a first morning void when possible.

Table 7 shows the 24-hour urine collection procedure by study visit.

Table 7: 24-hour Urine Collection Procedure by Study Visit

Study Visit and Urine Collection Window	Number of Collections to Schedule	Validity Requirement Prior to Dosing (see Sec 6.3.1.1)	Option for Catheterized Collection?	Notes
Screening (within 60-day period)	3	2 valid collections prior to dosing	No	Supervised collections are encouraged unless patient already familiar with collection procedure. If any collections are invalid, the remaining collections for screening must be supervised.
Month 6 and Month 12 (within 14 days prior to dosing)	3	2 valid collections prior to dosing	Yes	If a patient has had ≥ 2 prior invalid collections, all 3 collections must be supervised. At least 2 valid collections must be obtained prior to dosing. If any collections for the timepoint are invalid, the remaining collections for the timepoint must be supervised.
Interim Monthly Visits with Dosing (Months 1-3 and Months 7-9 [within 7 days prior to dosing])	1	No	Yes	If invalid collection is obtained for the timepoint, single repeat collection must be supervised. Repeat collection, if necessary, is to be completed within ± 7 days of dosing.
Interim Monthly Visits Without Dosing (Month 4 and Month 5 [within 7 days prior to visit])	1	No	Yes	If invalid collection is obtained for the timepoint, single repeat collection must be supervised. Repeat collection, if necessary, is to be completed within ± 7 days of the visit.
Visits after Month 12 (within 14 days prior to visit)	1	No	Yes	If collection is invalid for the timepoint, single repeat collection must be obtained within ± 14 days of the visit. Dose should not be held if validity results unknown prior to dosing.
Safety Follow-up Visits (within ± 7 days of visit)	1	No	Yes	Repeat collections are optional.

Abbreviations: Sec=section

Notes:

- Any or all of the 24-hour urine collections may be conducted supervised. If 24-hour urine is not a supervised collection, patients may either bring 24-hour urine collections to the clinic or have it couriered to the designated laboratory.
- Optional catheterized collections are permitted at any visit after initial study drug administration at the discretion of the Investigator with agreement of patient and/or legal guardian, if applicable.

6.3.1.1. Validity Criteria for 24-hour Urine Collections

A urine collection will be considered valid if each of the following criteria are met:

- The collection is between 22-26 hours in duration between the initial discarded void and the last void or attempt to void.
- No voids are missed between the start and end time of the collection as indicated by the patient's urine collection diary.
- The 24-hour creatinine content is at least 10 mg/kg as assessed by the central laboratory.

6.3.1.2. Urinary Oxalate:Creatinine Ratio

Urine oxalate:creatinine ratios will be calculated from the oxalate and creatinine levels measured in the 24-hour urine collections to assess the PD effect of lumasiran on urinary oxalate:creatinine ratio. Urinary oxalate:creatinine ratios from random spot urine collections will also be measured.

6.3.2. Estimated Glomerular Filtration Rate

Blood samples for the assessment of eGFR will be obtained at the time points specified in the Schedules of Assessment ([Table 1](#) and [Table 2](#)). eGFR (mL/min/1.73m²) will be calculated to assess renal function during the study. The calculation will be based on the Modification of Diet in Renal Disease (MDRD) formula for patients ≥ 18 years of age and the Schwartz Bedside Formula for patients < 18 years of age at screening (Appendix [10.1](#)).[[Levey 2009](#); [Schwartz 2009](#)]

6.3.3. Renal Stone Events

A renal stone event is defined as an event which includes at least one of the following:

- Visit to healthcare provider (eg, outpatient clinic, urgent care, emergency department, procedure) because of a renal stone
- Medication for renal colic
- Stone passage
- Macroscopic hematuria due to a renal stone

All relevant clinical information pertaining to the event should be obtained, including laboratory values, medical records, discharge summaries, and medical test results.

Since renal stone events are recorded as an efficacy assessment for lumasiran, these will not be treated as AEs or SAEs. However, if a patient experiences other AEs or SAEs during a renal stone event, they should be reported (see Section [6.5.7.1](#)).

6.3.4. Sample Analysis

All PD assessments will be analyzed centrally. Details on the blinding of study results are provided in Section [3.6](#).

Details regarding the processing and aliquoting of samples for storage and analyses will be provided in the Laboratory Manual.

6.4. Pharmacokinetic Assessments

Blood samples will be collected for the assessment of lumasiran PK parameters including metabolites (as necessary) at the time points indicated in the Schedules of Assessments ([Table 1](#) [Table 2](#)). A detailed schedule of time points for the collection of blood samples for PK analysis is in [Table 3](#) and [Table 4](#) (for patients at East Asian Study Centers; see Section [6.4.1](#)).

The concentration of lumasiran in blood samples will be determined using a validated assay. Details regarding sample volumes to be collected, and the processing, shipping, and analysis of the samples will be provided in the Laboratory Manual.

6.4.1. Pharmacokinetic Assessments in Patients at East Asian Study Centers

In patients who are enrolled at East Asian sites, which include sites in China, Korea, Japan, Taiwan, and Hong Kong, blood and urine samples for PK analysis will be collected at the time points indicated in [Table 4](#) and [Table 5](#).

Plasma PK parameters such as C_{max} , t_{max} , $t_{1/2\beta}$, AUC, CL/F, and V/F will be calculated for the lumasiran plasma concentration profiles. In addition, urine PK parameters will be calculated using pooled urine samples collected over 24 hours from patients at East Asian study centers according to the schedule provided in [Table 5](#).

6.5. Safety Assessments

The assessment of safety during the study will consist of the surveillance and recording of AEs including serious adverse events (SAEs), recording of concomitant medication and measurements of vital signs, weight and height, physical examination, and electrocardiogram (ECG) findings and laboratory tests.

Safety will be monitored over the course of the study by a DMC as described in Section [3.7](#).

6.5.1. Vital Signs

Vital signs will be measured as specified in the Schedules of Assessments ([Table 1](#) and [Table 2](#)) and include blood pressure, heart rate, body temperature, and respiratory rate. Vital signs will be measured predose, when applicable. On Day 1 and Month 6 only, vital signs will also be measured 30 ± 10 minutes postdose. When vital signs and blood sample collection occur at the same time, vital signs should be performed before blood samples are drawn, where possible. Vital signs should be measured in the seated or supine position, after the patient has rested comfortably for 10 minutes. Blood pressure should be taken using the same arm. Body temperature in degrees Celsius will be obtained via oral, tympanic, or axillary methods. Heart rate will be counted for a full minute and recorded in beats per minute, and respiration rate will be counted for a full minute and recorded in breaths per minute.

Additional vital sign assessments, as medically indicated, may be added at the discretion of the Investigator, or as per DMC advice.

Vital signs results will be recorded in the eCRF.

6.5.2. Weight and Height

Height will be measured in centimeters. For patients <18 years of age at the study visit, height will be measured in triplicate. Body weight will be measured in kilograms. Height and body weight measurements will be collected as specified in the Schedules of Assessments ([Table 1](#) and [Table 2](#)) and will be recorded in the eCRF. Body weight collected within 4 months prior to the study drug dose or the predose weight collected on the study visit day or dosing day will be used for dose calculations.

6.5.3. Physical Examination

Full and symptom-directed physical examinations will be conducted according to the Schedules of Assessments ([Table 1](#) and [Table 2](#)); if a physical examination is scheduled for a dosing visit, it should be conducted prior to dosing. Full physical examinations will include the examination of the following: general appearance; head, eyes, ears, nose and throat; respiratory, cardiovascular, gastrointestinal, musculoskeletal, and dermatological systems; thyroid; lymph nodes; and neurological status. If a visit is conducted offsite (eg, home), a body system assessment may be performed in lieu of a physical examination.

Symptom-directed physical examinations will be guided by evaluation of changes in symptoms, or the onset of new symptoms, since the last visit.

Physical examination notes regarding any observed abnormalities will be recorded in the eCRF.

6.5.4. Electrocardiogram

12-lead ECGs will be obtained, as specified in the Schedules of Assessments ([Table 1](#) and [Table 2](#)). Specific timepoints and details regarding the method of ECG acquisition (local/singlicate or central/triplicate) are provided in [Table 3](#) and [Table 4](#). Patients should be supine for at least 10 minutes before each ECG is obtained. Triplicate 12-lead ECGs will have readings approximately 5 minutes apart and will be centrally read.

When ECG and blood sample collection occur at the same time, ECGs should be performed before blood samples are drawn, when possible.

The Investigator or qualified designee will review all ECGs to assess whether the results have changed since the Baseline visit and to determine the clinical significance of the results. These assessments will be recorded in the eCRF. Additional ECGs may be collected at the discretion of the Investigator, or as per DMC advice. Recordings will be archived according to the Study Manual.

During periods of time when the COVID-19 pandemic impedes the ability of patients to travel to the study site, ECG assessments may be completed up to 7 months after the intended timepoint for visits at Month 12 and later.

6.5.5. Renal Ultrasound

Renal ultrasounds will be obtained as specified in the Schedules of Assessments ([Table 1](#) and [Table 2](#)). Renal ultrasound will be performed according to instructions provided in the Study Manual in a standardized manner. Renal ultrasounds will be reviewed centrally and those obtained at Screening and Month 6 will be read in a blinded manner.

During periods of time when the COVID-19 pandemic impedes the ability of patients to travel to the study site, renal ultrasounds may be completed up to 7 months after the intended timepoint for visits at Month 12 and later.

6.5.6. Clinical Laboratory Assessments

The following clinical laboratory tests will be evaluated by a central laboratory. Specific instructions for transaminase elevations are provided in Section [5.2.3.1](#). For any other unexplained clinically relevant abnormal laboratory test occurring after study drug administration, the test should be repeated and followed up at the discretion of the Investigator, or as per DMC advice, until it has returned to the normal range or stabilized, and/or a diagnosis is made to adequately explain the abnormality. Additional safety laboratories and assessments as indicated by the clinical situation may be requested. Clinical laboratory assessments are listed in [Table 8](#) and will be assessed as specified in the Schedule of Assessments ([Table 1](#) and [Table 2](#)).

While local laboratory results may be used for urgent clinical and dosing decisions, on the day of the clinic visit assessments, all laboratory assessments specified in [Table 8](#) which are performed at the clinic should also be sent in parallel to the central laboratory. Central laboratory results (once available) should be used for subsequent clinical and dosing decisions in the case of discrepant local and central laboratory results on samples drawn on the same day.

For any safety event or laboratory abnormality, additional laboratory assessments, imaging, and consultation may be performed for clinical evaluation and/or in consultation with the Medical Monitor; results may be collected and should be included in the clinical database.

Clinical laboratory assessments may be collected at the clinical site or at a location other than the clinical study center by a trained healthcare professional.

Table 8: Clinical Laboratory Assessments

Hematology	
Complete blood count with differential	
Serum Chemistry	
Sodium	Potassium
BUN	Phosphate
Creatinine and eGFR (using the MDRD formula for adults [≥ 18 years of age at screening] or the Bedside Schwartz formula for children <18 years at screening)	Albumin
Uric acid	Calcium
Total protein	Carbon dioxide
Glucose	Chloride
Pyridoxine (vitamin B6) ^a	
Liver Function Tests	
AST	ALP
ALT	Bilirubin (total and direct)
Urinalysis	
Visual inspection for appearance and color	Bilirubin
pH (dipstick)	Nitrite
Specific gravity	RBCs
Ketones	Urobilinogen
Albumin	Leukocytes
Glucose	Microscopy (if clinically indicated)
Protein	

Abbreviations: ALP=alkaline phosphatase; ALT=alanine transaminase; AST=aspartate transaminase; BUN=blood urea nitrogen; eGFR=estimated glomerular filtration rate; MDRD=modification of diet in renal disease; PH1=primary hyperoxaluria type 1; RBC=red blood cell

^aPyridoxine (vitamin B6) is required through Month 18 and only for patients receiving vitamin B6 for the treatment of PH1. On days when a blood sample for pyridoxine will be collected, patients should be instructed not to take vitamin B6 within 6 hours prior to blood sample collection.

6.5.6.1. Immunogenicity

Blood samples will be collected to evaluate antidrug antibodies. Blood samples for antidrug antibody testing must be collected before study drug administration as specified in the Schedules of Assessments (Table 1 and Table 2). A blood sample to evaluate antidrug antibodies will be collected at the Early Termination (ET) visit, if applicable.

Details regarding the processing, shipping, and analysis of the samples will be provided in the Laboratory Manual.

6.5.6.2. Pregnancy Testing

A pregnancy test will be performed for women of child-bearing potential, and for pediatric/adolescent females upon initiation of menarche. A serum pregnancy test will be performed at Screening or upon initiation of menarche, if applicable, and urine pregnancy tests will be performed thereafter per the Schedule of Assessments and any time pregnancy is suspected. More frequent pregnancy testing may be performed where required per local requirements. The results of the pregnancy test must be known before study drug administration. Patients who are pregnant at Screening are not eligible for study participation. Any woman with a positive urine pregnancy test, subsequently confirmed by a positive serum pregnancy test, during the study will be discontinued from study drug, but will continue to be followed for safety. Patients determined to be pregnant while on study will be followed at least until the pregnancy outcome is known (see Section [6.5.7.7](#) for follow-up instructions).

Pregnancy testing may be performed offsite by a patient/caregiver if the patient/caregiver will be administering study drug.

6.5.6.3. Additional Liver Function Assessments

Additional laboratory assessments will be performed in patients who experience any LFT abnormalities as outlined in Section [5.2.3.1](#). Following the occurrence of elevated liver transaminases or other LFT abnormalities per central laboratory, all assessments in [Table 9](#) will be performed one time, as well as hematology, serum chemistry, LFTs from [Table 8](#), and coagulation parameters, and other assessments or evaluations per Investigator discretion, as appropriate.

Monitoring, including criteria for withholding the study drug, are described in Section [5.2.3.1](#).

Table 9: Hepatic Assessments in Patients Who Experience Elevated Transaminases

Extended Hepatic Panel	
Herpes Simplex Virus 1 and 2 antibody IgM, IgG	Herpes Zoster Virus IgM, IgG
HIV 1 and 2 ^a	HHV-6
Cytomegalovirus antibodies, IgM, IgG	HBs Ag, HBc antibody IgM and IgG
Anti-nuclear antibodies	Epstein-Barr Virus antibodies, IgM and IgG
Anti-smooth muscle antibodies	Anti-mitochondrial antibodies
HCV antibody	HAV antibody IgM
HCV RNA PCR – qualitative and quantitative	HEV antibody IgM
Imaging	
Abdominal ultrasound with Doppler flow (or CT or MRI) including right upper quadrant	
Focused Medical and Travel History	
Use of any potentially hepatotoxic concomitant medications, including over the counter medications and herbal remedies	Alcohol consumption
Other potentially hepatotoxic agents including any work-related exposures	Recent travels to areas where hepatitis A or E is endemic

Abbreviations: CT=computed tomography; HAV=hepatitis A virus; HBc=hepatitis B core; HBsAg=hepatitis B virus surface antigen; HCV=hepatitis C virus; HEV=hepatitis E virus; HHV-6=human herpesvirus 6; HIV=human immunodeficiency virus; IgG=immunoglobulin G antibody; IgM=immunoglobulin M antibody; MRI=magnetic resonance imagery; PCR=polymerase chain reaction; RNA=ribonucleic acid.

Note:

- All assessments will be measured in central laboratory. The full panel of assessments should only be performed once; individual assessments may be repeated, as needed.

^a HIV testing will not be performed where prohibited by local regulations.

6.5.6.4. Maximum Blood Volume

The maximum blood volume, which will be collected from pediatric patients over the course of the study, will be based on age and weight and will not exceed those specified in [Table 10](#) from the Feinstein Institute for Medical Research Human Subject Protection Program Guidance Document (Section 10.2 in the Appendix).[\[Feinstein Institute 2013\]](#) Collections per the SOA do not exceed the maximum 24-hour or 30-day volume limits for a 15 kg child who is not at an East Asian site. At East Asian sites, if a patient weighs less than 30 kg, then PK blood samples should be limited to 1 ml at each time point and the blood samples for exploratory analyses should not be drawn.

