10.2. Blood Volume Limits in Pediatric Patients

The maximum blood volume, which will be collected from pediatric patients over the course of the study, will be based on age and weight and will not exceed those specified in [Table 10](#), which was adapted from the Feinstein Institute for Medical Research Human Subject Protection Program Guidance Document.

Table 10: Maximum Allowable Total Blood Volume Collection Chart

Body Weight (kg)	Body Weight (lbs)	Total blood volume (mL)	Maximum allowable volume in a 24 hour		Total volume collected in a 30-day period	
			2.5% of total blood volume (mL)	3% of total blood volume (mL)	5% of total blood volume (mL)	10% of total blood volume (mL)
1	2.2	100	2.5	3	5	10
2	4.4	200	5	6	10	20
3	6.6	240	6	7.2	12	24
4	8.8	320	8	9.6	16	32
5	11	400	10	12	20	40
6	13.2	480	12	14.4	24	48
7	15.4	560	14	16.8	28	56
8	17.6	640	16	19.2	32	64
9	19.8	720	18	21.6	36	72
10	22	800	20	24	40	80
11-15	24-33	880-1200	22-30	26.4-36	44-60	88-120
16-20	35-44	1280-1600	32-40	38.4-48	64-80	128-160
21-25	46-55	1680-2000	42-50	50.4-60	64-100	168-200
26-30	57-66	2080-2400	52-60	62.4-72	104-120	208-240
31-35	68-77	2480-2800	62-70	74.4-84	124-140	248-280
36-40	79-88	2880-3200	72-80	86.4-96	144-160	288-320
41-45	90-99	3280-3600	82-90	98.4-108	164-180	328-360
46-50	101-110	3680-4000	92-100	110.4-120	184-200	368-400
51-55	112-121	4080-4400	102-110	122.4-132	204-220	408-440
56-60	123-132	4480-4800	112-120	134.4-144	224-240	448-480
61-65	134-143	4880-5200	122-130	146.4-156	244-260	488-520
66-70	145-154	5280-5600	132-140	158.4-168	264-280	528-560
71-75	156-165	5680-6000	142-150	170.4-180	284-300	568-600
76-80	167-176	6080-6400	152-160	182.4-192	304-360	608-640
81-85	178-187	6480-6800	162-170	194.4-204	324-340	648-680
86-90	189-198	6880-7200	172-180	206.4-216	344-360	688-720
91-95	200-209	7280-7600	182-190	218.4-228	364-380	728-760
96-100	211-220	7680-8000	192-200	230.4-240	384-400	768-800

Adapted from <http://www.feinsteininstitute.org/wp-content/uploads/2013/02/Maximum-Blood-Draw-Limits.pdf>. [Feinstein Institute 2013]

**ALN-GO1-003 PROTOCOL AMENDMENT 3
SUMMARY OF CHANGES DATED 06 MAY 2020**

**ILLUMINATE-A: A Phase 3 Randomized, Double-Blind, Placebo Controlled Study with
an Extended Dosing Period to Evaluate the Efficacy and Safety of Lumasiran in Children
and Adults with Primary Hyperoxaluria Type 1**

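### Two 30-day limits in the paediatric blood-volume table (Protocol Table 10) do not equal 5% of their own row's blood volume: 64 mL should be 84 mL, and 360 mL should be 320 mL

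*Protocol*

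**What the plan says.** Section 6.5.6.4 of the Protocol states that the maximum blood volume collected from paediatric patients over the study "will be based on age and weight and will not exceed those specified in" Table 10. Appendix 10.2 repeats the rule and prints the table, "which was adapted from the Feinstein Institute for Medical Research Human Subject Protection Program Guidance Document".

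Table 10 lists body weight, total blood volume and four limits. Two limits (2.5% and 3% of total blood volume) stand under "Maximum allowable volume in a 24 hour" and two (5% and 10%) under "Total volume collected in a 30-day period". The rows at issue are:

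- 21-25 kg: total blood volume 1680-2000 mL, 5% limit 64-100 mL.
- 76-80 kg: total blood volume 6080-6400 mL, 5% limit 304-360 mL.

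Section 6.5.6.4 adds that, outside East Asian sites, scheduled collections "do not exceed the maximum 24-hour or 30-day volume limits for a 15 kg child". It does not say which column was used for that statement. At East Asian sites, patients under 30 kg have each PK sample limited to 1 mL and give no exploratory blood samples. The section does not say that the resulting total meets the limits.

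**The concern.** Each entry in the 5% column should be 5% of the blood volume printed two or three columns to its left, and the limits should rise with weight. Two entries fail both tests. Because section 6.5.6.4 takes in the table by reference, these are wrong safety thresholds and not background typing slips. One lets a site draw more than the column's own rule allows. The other forbids volumes that the rule would permit.

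The cap is a working constraint in this trial. Enrolment starts at age 6, and the Amendment 3 rationale for dropping routine coagulation tests cites the tighter blood-volume limits in children.

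**Working it through.** **Inputs.** All come from Table 10 in Appendix 10.2. The formula is: limit = column percentage × total blood volume of the row, applied to both ends of each range.

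**Full recomputation.** Ten single-weight rows (1 to 10 kg) and 18 range rows (11-15 to 96-100 kg), with four percentage columns, give 10 × 4 + 18 × 2 × 4 = 184 values. Of these, 182 reproduce exactly. Both failures lie in the 5% column, where 44 of 46 values are right.

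**The two failures.**

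| Weight | Total blood volume | 5% computed | Printed | Difference | Printed value as % of blood volume |
|---|---|---|---|---|---|
| 21 kg | 1680 mL | 0.05 × 1680 = 84 mL | 64 mL | -20 mL (24% below 84) | 64 / 1680 = 3.8% |
| 80 kg | 6400 mL | 0.05 × 6400 = 320 mL | 360 mL | +40 mL (12.5% above 320) | 360 / 6400 = 5.6% |

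The other end of each range is right: 0.05 × 2000 = 100 mL and 0.05 × 6080 = 304 mL.

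**Check against neighbouring rows.** The 16-20 kg row runs 64-80 mL, so the printed limit falls from 80 mL at 20 kg to 64 mL at 21 kg. The 81-85 kg row runs 324-340 mL, so the whole of it lies below the 360 mL printed for 80 kg. With 84 and 320 the column rises with weight throughout.

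**Check within the same rows.** The other three columns agree with the printed blood volume. At 21 kg they give 42, 50.4 and 168 mL (2.5%, 3% and 10% of 1680). At 80 kg they give 160, 192 and 640 mL (the same percentages of 6400). The blood volumes are therefore right and the two 5% entries are wrong.

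**Where the errors could change a decision.** If the 5% column governs, the misprints matter only for a 30-day total above 64 and up to 84 mL at 21 kg, or above 320 and up to 360 mL at 80 kg. Scheduled draws outside East Asia can be placed against these windows through the 15 kg statement, assuming that the scheduled volume does not increase with body weight:

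- Statement checked against the 5% column: at 15 kg (1200 mL) the limit is 0.05 × 1200 = 60 mL. Scheduled draws of at most 60 mL stay under even the misprinted 64 mL.
- 10% column governs: the limits are 168-200 mL and 608-640 mL, both printed correctly, and the 5% misprints do not bind.
- At 80 kg, scheduled draws are at most 60 or 120 mL (0.10 × 1200), well short of 320 mL on either reading.

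One mixed case stays open: the statement was checked against the 10% column while a site applies the 5% column. The Protocol gives no per-visit volumes, so this case can be neither shown nor excluded.

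**The case against.** The strongest objection is that the errors may not be in the Protocol. The text was machine-read from PDF, and each failing value differs from the right one by a single digit that became a 6. This cannot be excluded without the page. It argues for looking at the page before editing. It does not explain the values away, since the other 182 recompute.

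The second objection is that neither error does visible harm. This largely stands. The 21 kg error is on the cautious side, no documented scenario reaches 320-360 mL in 30 days, and the neighbouring rows make both slips easy to spot. A reader might infer that sites would omit scheduled samples in small children, or that the 21-25 kg band is where the youngest patients fall. The documents support neither. On the coherent readings, scheduled draws outside East Asia are unaffected, and there are no weight data for the population. What remains is unscheduled blood (the liver-test monitoring of Table 6, the one-time Table 9 panel, repeats of abnormal tests) and East Asian sites. There the Protocol already reduces sampling below 30 kg but makes no statement of compliance.

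A reader might also infer that two columns per period leave the cap undefined. The rule that volumes stay within the table's values can be read so that the lower column binds, which gives one number per period. The silence about the column is therefore missing detail more than an error. Nor are unscheduled draws left uncapped: the first sentence of 6.5.6.4 covers blood collected over the course of the study, and the 15 kg sentence claims only that the schedule fits.

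**Conclusion.** The point holds as a correction of two cells. In the text as supplied, the 30-day 5% limit is 20 mL too low at 21 kg and 40 mL too high at 80 kg. This follows from Table 10 alone, on the assumption that the extracted digits match the page.

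The consequence is small. It is limited to unscheduled draws or East Asian sites, and no breach or lost sample is shown for scheduled draws elsewhere. That judgement rests on the 15 kg statement in 6.5.6.4, which cannot be verified from the documents. Efficacy, analysis and sample size are untouched.

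The unnamed column is a secondary matter of clarity. For the Protocol's own 15 kg benchmark the limits are 30 or 36 mL per 24 hours and 60 or 120 mL per 30 days, and a reader cannot tell which pair was used.

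**What to change.** Check both cells against the source page of Appendix 10.2. If the page agrees with the extracted text, change the 5% entry for 21-25 kg to 84-100 mL and the 5% entry for 76-80 kg to 304-320 mL. Any site worksheet built from the table needs the same two changes.

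Optionally, add one sentence to 6.5.6.4 naming the 24-hour column and the 30-day column that govern, and confirm the 15 kg statement against them. The choice of column belongs to the clinical team.

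The cost is two table cells and at most one sentence. If the lower columns are named, the permitted volume becomes smaller for any site that has been applying the higher ones.
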